### 10.3.2 Safety Analyses

All safety analyses (see Table 10.3.2-1) will be performed on the treated population.

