**Expansion: Part 2A (Relatlimab, Nivolumab, and BMS-986205) and Part 2B (Relatlimab, Nivolumab, and Ipilimumab)**

Part 2 is the safety evaluation, tolerability, and cohort expansion of the triple combinations in distinct cohorts advanced malignant tumors to gather preliminary efficacy information. The doses to be administered are determined from Part 1A and Part 1B of the study. The recommended Phase 2 dose (RP2D) selected for Part 2 are as follows:

Part 2A: Relatlimab 160 mg Q4W, Nivolumab 480 mg Q4W, BMS-986205 100 mg QD

Part 2B: Relatlimab 160 mg Q4W, Nivolumab 480 mg Q4W, Ipilimumab 1 mg/kg Q8W

The tumor cohorts and regimens are:

- [REDACTED]

The dose-finding phase of the study (Part 1A and Part 1B) evaluates the safety and tolerability of relatlimab in combination with nivolumab and BMS-986205 (Part 1A) or nivolumab and ipilimumab (Part 1B) based on DLTs, using [REDACTED] and safety evaluation beyond the DLT phase. Any toxicities that occur beyond the DLT period will be accounted for in making dose level decisions and/or dose level modifications.

After the initial participants (approximately 3) are evaluated at the starting dose levels in Part 1A and Part 1B, additional increments of approximately 3 to 6 participants will be treated in the same cohort (or at the next dose level) [REDACTED]. At least 6 DLT-evaluable participants will be treated and assessed in the selected combination dose level before starting the cohort-expansion phase at the same dose. [REDACTED]

Prior to declaring the maximum tolerated dose, and in consultation with Investigators, the Sponsor has the option to expand any dose level previously established to be tolerable, in order to obtain additional experience or to investigate dose levels intermediate to those defined in the protocol.

Physical examinations, vital sign measurements, 12-lead electrocardiograms (ECGs), and clinical laboratory evaluations will be performed at selected times throughout the dose administration interval. Participants will be closely monitored for adverse events (AEs) throughout the study.

[REDACTED]

Continuous safety evaluation and tumor assessment [REDACTED] will guide the decision to treat a participant with additional cycles of study therapy if the participant has confirmed clinical benefit.

[REDACTED]

Participants with unconfirmed progressive disease, stable disease (SD), or partial response (PR) at the end of a given cycle will continue to the next treatment cycle.

[REDACTED]

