**Table 4-1: Objectives and Endpoints**

Objectives	Endpoints
Primary	

 
Part 1A and Part 1B: To determine the safety, tolerability, DLTs, and MTD of relatlimab administered in combination with nivolumab and BMS-986205 or nivolumab and ipilimumab in participants with advanced malignant tumors.
 
	
 
Incidence of clinical laboratory test abnormalities, AEs, SAEs, AEs meeting protocol-defined DLT criteria, AEs leading to discontinuation, and deaths.
 

 
Part 2A and Part 2B: To investigate safety and tolerability of relatlimab triple combinations in distinct cohorts of participants with advanced malignant tumors.
 
	
 
Incidence of clinical laboratory test abnormalities, AEs, SAEs, AEs leading to discontinuation, and deaths.
 

 
To investigate the antitumor activity of relatlimab triple combinations in participants with advanced malignant tumors.
 
	
 
ORR, DCR, and mDOR in participants with advanced malignant tumors.
 

Secondary	

 
To investigate the antitumor activity of relatlimab triple combinations in participants with advanced malignant tumors.
 
	
 
mPFS and PFSR at 6 and 12 months in participants with advanced malignant tumors.
 

Exploratory	

Abbreviations: AE = adverse event; DCR = disease control rate; DLT = dose-limiting toxicity; IgG = immunoglobulin G; [REDACTED]; mDOR = median duration of response; [REDACTED]; mPFS = median progression-free survival; MTD = maximum tolerated dose; ORR = overall response rate; [REDACTED]; PFSR = progression-free survival rate; [REDACTED]; SAE = serious adverse event; [REDACTED]

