## 7.2 Method of Treatment Assignment

All participants will be centrally assigned using an Interactive Response Technology (IRT) system; until this system is activated, enrollment may be manually managed by the Sponsor. Before the study is initiated, each user will receive log in information and directions on how to access the IRT.

Study treatment will be dispensed at the study visits per the Schedule of Activities ([Section 2](#)).

During the screening visit, the investigative site will call into the enrollment option of the IRT designated by BMS for assignment of a 5-digit participant number that will be unique across all sites. Enrolled participants, including those not dosed, will be assigned sequential participant numbers starting with [REDACTED]. The PID number will ultimately be comprised of the site number and participant number. For example, the first participant screened (ie, enrolled) at site number 1, will have a PID of [REDACTED]. Once it is determined that the participant meets the eligibility criteria following the screening visit, the investigative site will call the IRT to assign the participant into the open dose level.

Treatment assignments for participants eligible for both Part 1A and Part 1B or for melanoma participants in Part 2A or Part 2B will alternate among the parts, with consecutively screened participants assigned to different parts through IRT. If a treatment arm becomes overly enrolled because of screen failures in the alternate arm, it can be temporarily closed to allow enrollment in the alternate arm only. Once balance is achieved, the temporary hold can be lifted. If there are no openings available in the part to which the participant would be assigned by this algorithm, the participant will be assigned to the next open part/cohort until respective dose levels or cohorts have completed accrual according to principles outlined in [Section 5.1.2](#).

Participants will not be replaced if they are discontinued from the study secondary to an AE unless the AE can be determined to be unrelated to treatment.

Participants not evaluable for DLT will be replaced. Participants not evaluable for PD endpoints may be replaced at the discretion of the Sponsor.

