## **10 STATISTICAL CONSIDERATIONS**

### **10.1 Sample Size Determination**

## 10.2 Populations for Analyses

For purposes of analysis, the following populations are defined:

Population	Description
Enrolled	All participants who sign informed consent and are registered into the IRT
Treated	All participants who take at least 1 dose of study treatment
Response-evaluable	All treated participants with measurable disease at baseline and 1 of the following: a) at least 1 post-baseline tumor assessment; b) clinical progression, or c) death
[REDACTED]	[REDACTED]
[REDACTED]	[REDACTED]
[REDACTED]	[REDACTED]

Abbreviations: IRT = interactive response technology; [REDACTED].

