**Table 10.3.2-1: Overview of Safety Analysis Methods**

Endpoint	Statistical Analysis Methods
Incidence of AEs, SAEs, AEs meeting protocol-defined DLT criteria, AEs leading to discontinuation and deaths AEs will be graded according to CTCAE v5.0	DLT rate by dose level; frequency distribution of treated participants with AE using the worst CTC grade. Participants will only be counted (1) once at the PT level, (2) once at the SOC level, and (3) once in the “total participant” row at their worst CTC grade, regardless of SOC or PT.
Incidence of clinical laboratory test abnormalities Laboratory values will be graded according to CTCAE v5.0	Laboratory shift table using the worst CTC grade on treatment per participant.

Abbreviations: AE = adverse event; CTC = Common Terminology Criteria; CTCAE = Common Terminology Criteria for Adverse Events; DLT = dose-limiting toxicity; PT = preferred term; SAE = serious adverse event; SOC = system organ class.

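### Section 10.3.2 puts the Part 1 DLT rate on all treated participants rather than DLT-evaluable ones, which dilutes the reported rate at any dose level with replacements

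*Combined protocol and SAP*

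**What the plan says.** Table 4-1 gives the primary endpoint for Part 1A and Part 1B as "Incidence of clinical laboratory test abnormalities, AEs, SAEs, AEs meeting protocol-defined DLT criteria, AEs leading to discontinuation, and deaths". DLT incidence is therefore part of a primary Part 1 endpoint.

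Section 10.3.2 sets one population for all safety work: "All safety analyses (see Table 10.3.2-1) will be performed on the treated population". In Table 10.3.2-1 the method for the adverse event endpoints begins "DLT rate by dose level; frequency distribution of treated participants with AE using the worst CTC grade". Section 10.2 defines the treated population as "All participants who take at least 1 dose of study treatment", with no condition on completing the DLT period or on exposure within it.

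Elsewhere the protocol treats DLT evaluability as a separate status. Section 7.2 says "Participants not evaluable for DLT will be replaced". The Protocol Summary says "At least 6 DLT-evaluable participants will be treated and assessed in the selected combination dose level before starting the cohort-expansion phase at the same dose".

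**The concern.** The design counts DLT-evaluable participants, while the stated analysis divides by everyone dosed. A participant who took a dose but did not become evaluable is replaced for dose-finding purposes, yet under Section 10.3.2 stays in the denominator of the DLT rate. If such a participant cannot by definition have had a DLT, the effect runs one way and the reported rate is too low.

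The dilution also depends on how many participants were replaced at each dose level. Two levels with the same DLT experience among evaluable participants would show different rates if their replacement counts differed. A reader of the study report would take the figure as the DLT risk at that dose.

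**Working it through.** The visible text states no DLT rate, target rate or DLT count, and the sample-size text in Section 10.1 is redacted. There is thus no plan figure to reproduce. The check has two steps.

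**Step 1: does the rule cover the DLT rate?**

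- Section 10.3.2 covers every analysis in Table 10.3.2-1 and states no exception.
- The DLT rate by dose level is in that table, with no denominator of its own.
- By contrast, Section 10.3.1 names a second population (response-evaluable) for some interim efficacy analyses. Section 10.3.2 names none.

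As written, the denominator is therefore all treated participants at the dose level.

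**Step 2: what does that do to the rate?**

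Let x be the number of participants with a DLT, e the number of DLT-evaluable participants, and m the number treated but not evaluable, and so replaced.

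- Rate on evaluable participants: x / e.
- Rate under Section 10.3.2: x / (e + m).
- Relative change: e / (e + m) − 1.

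Inputs:

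- e = 6 is the stated minimum at the selected dose (Protocol Summary). e = 12 is an assumption, to show a larger dose level.
- m = 0 to 3 is an assumption; the documents give no replacement counts.
- x = 1, 2 or 4 is an assumption; the documents give no DLT counts.
- Every participant with a DLT is assumed to count as evaluable, so the m replaced participants add nothing to x.

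| e | x | m = 0 | m = 1 | m = 2 | m = 3 |
|---|---|---|---|---|---|
| 6 | 1 | 1/6 = 16.7% | 1/7 = 14.3% | 1/8 = 12.5% | 1/9 = 11.1% |
| 6 | 2 | 2/6 = 33.3% | 2/7 = 28.6% | 2/8 = 25.0% | 2/9 = 22.2% |
| 12 | 4 | 4/12 = 33.3% | 4/13 = 30.8% | 4/14 = 28.6% | 4/15 = 26.7% |

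The relative change at e = 6 is 6/7 − 1 = −14.3%, 6/8 − 1 = −25.0% and 6/9 − 1 = −33.3% for m = 1, 2 and 3. At e = 12 it is −7.7%, −14.3% and −20.0%. At m = 0 the two rates are the same.

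For scale, the exact (Clopper-Pearson) 95% interval for 2/6 runs from 4.3% to 77.7%. The shift is small against the sampling uncertainty, but it is systematic and avoidable.

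**The case against.** The best defence is that Section 10.3.2 is a loose umbrella sentence. Table 10.3.2-1 is titled an overview, Section 10.3 calls itself a summary, and the SAP is to be finalized before database lock and could name the right denominator. Within the table cell, the word treated attaches to the adverse event frequencies after the semicolon, not to the DLT rate before it. Three rows of the population table in Section 10.2 are redacted, and one may define a DLT-evaluable set.

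Part of this stands: nobody can say that the protocol lacks a DLT-evaluable population, and the drafters may not have intended a treated denominator. But the sentence in Section 10.3.2 is visible and has no exception. A DLT-evaluable set defined elsewhere would not alter it, and a SAP that used one would depart from the protocol text.

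A reader might infer three stronger points that the documents do not support:

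- **The dose decision is compromised, or used a different rate.** The Protocol Summary sets a minimum number of evaluable participants; it does not state a rate used for decisions. Decisions also drew on posterior inference from a redacted source, toxicities after the DLT period and other data. No mismatch can be shown.
- **Part 2 participants at the same dose will be pooled into the rate.** Section 10.3 says summaries are generally by dose level, cohort and indication, which points toward separate presentation.
- **The replacement rules contradict each other.** Section 7.2 also says "Participants will not be replaced if they are discontinued from the study secondary to an AE", unless the event is unrelated to treatment. That sentence concerns leaving the study. Whether someone who stops within the DLT period for a related event that is not a DLT is non-evaluable depends on criteria that are not visible. The DLT sentence can also be read as the specific rule that governs.

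**Conclusion.** The point holds as a defect in the stated denominator. Section 10.3.2 gives a diluted Part 1 DLT rate at any dose level where treated participants were replaced as non-evaluable. At the minimum of 6 evaluable participants, the relative fall would be 14.3%, 25.0% or 33.3% for 1, 2 or 3 replacements. With no replacements there is none.

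This rests on two assumptions. First, a participant with a DLT counts as evaluable; the definition cannot be seen, and the downward direction depends on it. Second, the DLT and replacement counts are illustrative.

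The consequence is limited to a descriptive rate. Part 1 formally tests no hypothesis (Section 3.1.1), and the recommended Phase 2 doses have already been selected. It is still worth correcting, because DLT incidence belongs to a primary endpoint.

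**What to change.** In Section 10.3.2 and Table 10.3.2-1, and in the SAP, add one exception, for example:

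*All safety analyses use the treated population, except the Part 1 DLT rate, which is calculated by regimen and dose level among DLT-evaluable participants as defined in this protocol.*

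Refer to the protocol's own definition of evaluable rather than writing a new one, which could conflict with text that is redacted here. For each dose level, also report how many treated participants were not DLT-evaluable, and why, so that a reader can work out either rate.

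The cost is a sentence in each place and one small table or listing. Evaluability already has to be determined to apply the replacement rule, so no new data should be needed. The one downside for the sponsor is that the reported DLT rate may be slightly higher.

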**Table 10.3.2-1: Overview of Safety Analysis Methods**

Endpoint	Statistical Analysis Methods
Incidence of AEs, SAEs, AEs meeting protocol-defined DLT criteria, AEs leading to discontinuation and deaths AEs will be graded according to CTCAE v5.0	DLT rate by dose level; frequency distribution of treated participants with AE using the worst CTC grade. Participants will only be counted (1) once at the PT level, (2) once at the SOC level, and (3) once in the “total participant” row at their worst CTC grade, regardless of SOC or PT.
Incidence of clinical laboratory test abnormalities Laboratory values will be graded according to CTCAE v5.0	Laboratory shift table using the worst CTC grade on treatment per participant.

Abbreviations: AE = adverse event; CTC = Common Terminology Criteria; CTCAE = Common Terminology Criteria for Adverse Events; DLT = dose-limiting toxicity; PT = preferred term; SAE = serious adverse event; SOC = system organ class.

### 10.3.4 Interim Analyses

The Statistical Analysis Plan will further describe the planned interim analyses.

## **12 APPENDICES**

## APPENDIX 1 ABBREVIATIONS AND TRADEMARKS

Term	Definition
1L	first-line
2L	second-line
ACLS	advanced cardiac life support
ADA	anti-drug antibody
AE	adverse event
AESOI	adverse events of special interest
AI	accumulation index
AI_AUC	AUC Accumulation Index; ratio of AUC(TAU) at steady state to AUC(TAU) after the first dose
AI_Cmax	Cmax Accumulation Index; ratio of Cmax at steady state to Cmax after the first dose
AI_Ctau	Ctau Accumulation Index; ratio of Ctau at steady state to Ctau after the first dose
AIDS	acquired immunodeficiency syndrome
	
ALT	alanine aminotransferase
ANC	absolute neutrophil count
ANOVA	analysis of variance
AST	aspartate aminotransferase
AT	aminotransaminase
AUC	area under the concentration-time curve
AUC(INF)	area under the concentration-time curve from time zero extrapolated to infinite time
AUC(0-T)	area under the concentration-time curve from time zero to the time of the last quantifiable concentration
AUC(TAU)	area under the concentration-time curve in one dosing interval
A-V	atrioventricular
$\beta$ -hCG	beta-human chorionic gonadotrophin
BICR	blinded independent clinical review
BID, bid	bis in die, twice daily
BLQ	below limit of quantification

Term	Definition
BMI	body mass index
BMS	Bristol-Myers Squibb Company
BOR	best overall response
BP	blood pressure
BUN	blood urea nitrogen
C	cycle
C12	concentration at 12 hours
C24	concentration at 24 hours
Ca ++	calcium
Cavg	average concentration
Cavgss	time-averaged steady-state concentration
CBC	complete blood count
CD	cluster of differentiation
CEA	carcinoembryonic antigen
Cexpected-tau	expected concentration in a dosing interval
CFR	Code of Federal Regulations
CI	confidence interval
Cl 	chloride
CL	clearance
CL/F	apparent clearance
CLss	clearance at steady-state
cm	centimeter
Cmax	maximum observed concentration
Cmaxss	maximum observed steady-state concentration
Cmin	minimum observed concentration
Cminss	minimum observed steady-state concentration
CNS	Central nervous system
CONSORT	Consolidated Standards of Reporting Trials
COVID-19	coronavirus disease 2019

Term	Definition
CR	complete response
CRC	colorectal cancer
CrCl	creatinine clearance
CRF	Case Report Form, paper or electronic
CT	computed tomography
CTAg	clinical trial agreement
CTC	common terminology criteria
CTCAE	Common Terminology Criteria for Adverse Events
ctDNA	circulating tumor DNA
CTLA-4	cytotoxic T-lymphocyte-associated protein-4
cTnI	cardiac troponin I
cTnT	cardiac troponin T
Ctrough	trough observed plasma concentration
CV	coefficient of variation
CYP	cytochrome p-450
D	day
DCR	disease control rate
D/C	discontinue
DIL	Dear Investigator Letter
DILI	drug-induced liver injury
dL	deciliter
DLT	dose limiting toxicity
DMC	data monitoring committee
DoR	duration of response
DRESS	drug reaction with eosinophilia and systemic symptoms
DSM IV	Diagnostic and Statistical Manual of Mental Disorders (4 th Edition)
EA	extent of absorption
EC50	half-maximal effective concentration
ECG	electrocardiogram

Term	Definition
ECOG	Eastern Cooperative Oncology Group
eCRF	electronic case report form
EDC	electronic data capture
EEG	electroencephalogram
eg	exempli gratia (for example)
eGFR	estimated glomerular filtration rate
██████	████████████████████
ELISA	enzyme-linked immunosorbent assay
EOI	end of infusion
EOT	end of treatment
ESR	Expedited Safety Report
F	bioavailability
FDA	Food and Drug Administration
FDC	Fixed-dose combination
██████	████████████████████
FSH	follicle stimulating hormone
FU/FUP	follow-up
g	gram
G6PD	glucose-6-phosphate dehydrogenase
GBS	Guillain-Barre syndrome
██████	████████████████████
GCP	Good Clinical Practice
Geo.	geometric
GFR	glomerular filtration rate
GGT	gamma-glutamyl transferase
h	hour
HBsAg	hepatitis B surface antigen
HBV	hepatitis B virus
HCC	hepatocellular carcinoma
hCG	human chorionic gonadotropin

Term	Definition
HCV	hepatitis C virus
HCO 3 	bicarbonate
HIV	human immunodeficiency virus
HPV	human papillomavirus
HR	heart rate
HRT	hormone replacement therapy
HuMAb	human monoclonal antibody
hWB	human whole blood
IB	Investigator's Brochure
IC50	half-maximal inhibitory concentration
ICD	International Classification of Diseases
ICF	informed consent form
ICH	International Conference on Harmonisation
IDO1	indoleamine 2,3-dioxygenase 1
ie	id est (that is)
IEC	Independent Ethics Committee
Ig	immunoglobulin
IgG	immunoglobulin G
IHC	immunohistochemistry
IMAE	immune-mediated adverse event
IMP	investigational medicinal products
IND	Investigational New Drug Exemption
IO	immuno-oncology
IP	investigational product
IPI	ipilimumab
IQR	interquartile range
IRB	Institutional Review Board
IRT	Interactive Response Technology

Term	Definition
IU	International Unit
IV	intravenous
K	slope of the terminal phase of the log concentration-time curve
K 3 EDTA	potassium ethylenediaminetetraacetic acid
K +	potassium
K d	dissociation constant
kg	kilogram
L	liter
LAG-3	lymphocyte activation gene 3
LAM	Lactation amenorrhea method
LCMS	liquid chromatography mass spectrometry
LDH	lactate dehydrogenase
ln	natural logarithm
LVEF	left ventricular ejection fraction
MAD	maximum administered dose
mDOR	median duration of response
MedDRA	Medical Dictionary for Regulatory Activities
mg	milligram
Mg ++	magnesium
MG	myasthenia gravis
MHC	major histocompatibility complex
MI	myocardial infarction
min	minute
mL	milliliter
MLR	mixed lymphocyte reaction
mmHg	millimeters of mercury
	
mPFS	median progression-free survival
MR	medical research
MRI	magnetic resonance imaging

Term	Definition
MS	mass spectrometry
MTD	maximum tolerated dose
MUGA	multiple-gated acquisition
µg	microgram
n	number of participants or observations
Na +	sodium
NA	not applicable
NCI	National Cancer Institute
ng	nanogram
NIVO	nivolumab
NSAID	nonsteroidal anti-inflammatory drug
NSCLC	non-small cell lung cancer
ORR	overall response rate
■	■
■	■
PBMC	peripheral blood mononuclear cell
PCR	polymerase chain reaction
■	■
PD-1	programmed death 1
PD-L1	programmed death-ligand 1
PD-L2	programmed death-ligand 2
PE	physical examination
PET	positron emission tomography
PFS	progression-free survival
PFSR	progression-free survival rate
PID	participant identification
■	■
PO	per os (by mouth route of administration)
■	■
PR	partial response

Term	Definition
PT	preferred term
QD	quaque die, once daily
Q2W	every 2 weeks
Q3W	every 3 weeks
Q4W	every 4 weeks
Q6W	every 6 weeks
Q8W	every 8 weeks
Q12W	every 12 weeks
R 	coefficient of determination
RBC	red blood cell
RCC	renal cell cancer
RECIST	Response Evaluation Criteria In Solid Tumors
RNA	ribonucleic acid
RO	receptor occupancy
RP2D	recommended Phase 2 dose
RT-PCR	reverse transcriptase-polymerase chain reaction
SAE	serious adverse event
SD	stable disease
SJS	Stevens-Johnson syndrome
SNP	single nucleotide polymorphism
SOC	system organ class
SOP	Standard Operating Procedures
sp.	species
SUSAR	suspected, unexpected serious adverse reaction
t	temperature

Term	Definition
T	time
T.Bili	total bilirubin
TAO	Trial Access Online, the BMS implementation of an EDC capability
TEN	toxic epidermal necrolysis
TID	ter in die, three times a day
Tmax	time to achieve maximum drug concentration
TnI	troponin I
TnT	troponin T
TRAE	treatment-related adverse event
TSH	thyroid-stimulating hormone
TTE	transthoracic echocardiogram
ULN	upper limit of normal
US	United States
UV	ultraviolet
VS	vital signs
Vss	volume of distribution at steady state
W	washout
WBC	white blood cell
WHO	World Health Organization
WOCBP	women of childbearing potential
WNOCBP	women not of childbearing potential
WWPS	Worldwide Patient Safety

